THE UNIVERSITY OF TEXAS

Protocol Abstract Page

Trial of Immune Reconstitution with Activated T-Cells in Patients with Chronic Lymphocytic Leukemia (CLL)

2014-0830

Core Protocol Information

Study Chairman:	[name]
Department:	Stem Cell Transplantation and Cellular Therapy
[contact]
Unit:	423
Full Title:	Trial of Immune Reconstitution with Activated T-Cells in Patients with Chronic Lymphocytic Leukemia (CLL)
Protocol Phase:	Phase II
Version Status:	Terminated 05/01/2018
Version:	07
Document Status:	Final

Abstract

Objectives:

Primary Objectives:

1. To assess the feasibility and safety of infusion of autologous activated T-cells in patients with chronic lymphocytic leukemia.

Secondary Objectives:

1. To study immune reconstitution following infusion of activated T-cells in patients with chronic lymphocytic leukemia.
2. To study the incidence of infections for up to 1 year following activated T cell infusion.
3. To study the overall response rates.

Rationale: (Be as concise as possible)

Despite significant advances in the management of CLL the disease remains incurable with standard chemo-immunotherapy. Moreover, even after complete responses, immunological abnormalities and minimal residual disease remain in most patients. Ultimately, chronic immunosuppression resulting in infectious complications occurs in over 80% of CLL patients and is a major cause of mortality. The pathogenesis of infections in patients with CLL is complex and multifactorial. CLL in itself can cause disease related immunosuppression that is compounded by the immunosuppression induced by agents

like fludarabine and alemtuzumab that are commonly used in the treatment of this disease. In preliminary studies, T cells activated using CD3xCD28 co-stimulatory technology have been shown to reverse some of these immune defects. This procedure is based on the roles of the CD3 signaling complex and CD28 receptor in the activation of T cells. In this study we plan to give *ex-vivo* stimulated T-cell infusion to patients with CLL. The hypothesis is that infusion of *ex-vivo* expanded T cells will influence quantitative and functional immune reconstitution in these patients. This should result in reduced rate of infectious complications, secondary malignancies, and may delay the time to disease progression.

Eligibility: (List All Criteria)

Inclusion:

- 1) All patients must have a diagnosis of CLL by immunophenotyping and flow cytometry analysis of blood or bone marrow. 1) Patients must meet criteria for treatment based on the criteria proposed by NCI-sponsored CLL Working Group to include at least one of the following: a) weight loss of more than 10% over the preceding 6 months; or, b) extreme fatigue attributable to progressive disease; or, c) fever or night sweats without evidence of infection; or, d) worsening anemia (Rai stage III) or thrombocytopenia (Rai stage IV); or, e) massive lymphadenopathy (>10 cm) or rapidly progressive lymphocytosis (lymphocyte doubling time <6 months); or, f) prolymphocytic or Richter's transformation; or, 2) Patients with CLL who have received at least one prior line of therapy; or, 3) Patients with CLL who have frequent infections and/or recurrent secondary cancers.
- 2) No active CNS disease.
- 3) All patients must have a Karnofsky Performance Score > 60%.
- 4) Calculated creatinine clearance (by Cockroft-Gault) of > 50 ml/min.
- 5) Patients must not have untreated or uncontrolled life-threatening infection.
- 6) Patients must sign informed consent.

Exclusion:

- 1) Receipt of glucocorticoids (with the exception of inhaled glucocorticoid steroids for the use of allergic rhinitis or pulmonary disease) within 2 weeks of registration.
- 2) Autoimmune disease related to CLL, e.g., idiopathic thrombocytopenic purpura (ITP) or autoimmune hemolytic anemia, is permitted if not requiring active treatment.

Are patients <18 years of age eligible to participate in this study? Yes No

Studies that include children must meet the criteria for inclusion.

http://www.fda.gov/ohrms/dockets/AC/04/briefing/4028B1_05_NIH-Inclusion%20of%20Children.doc
<http://www.hhs.gov/ohrp/policy/populations/children.html>

Are participants >65 years of age eligible to participate in this study? Yes No

Are pregnant women eligible to participate in this study? Yes No

Will the recruitment population at M. D. Anderson include persons who are incarcerated at time of enrollment (e.g., prisoners) or likely to become incarcerated during the study?

Yes No

Disease Group:

Leukemia

Treatment Agents/Devices/Interventions:

T cell therapy

Proposed Treatment/Study Plan:

Is treatment assignment randomized? Yes No

Is this a blinded or double-blinded study? Yes No

All eligible patients will have 250 cc of whole blood collected via phlebotomy.

The collected blood will be expanded ex-vivo by aAPCs. The expansion will take 14 days. The process can generate 2.5×10^9 to 1×10^{10} cells which will be formulated for infusion in 100-500 mL of human serum albumin infusion buffer. Cells for later additional infusions may be cryopreserved.

Patients will receive a single infusion of ex-vivo expanded autologous T-Cells. Optimal dose will be 1×10^{10} activated T cells (+/- 20%), however for patients who cannot achieve that dose, a lower dose of activated T cells that meets release criteria may be infused at the discretion of the Principal Investigator.

Additionally, patients who have been previously treated on study, and subsequently need additional infusions may be retreated with previously cryopreserved expanded cells at the same or lower dose level. Retreatment will occur 6-12 months after the first infusion as long as no DLT was noted with the first infusion. These patients will be only followed for toxicity. Patients who have previously experienced DLT will be removed from the study and will not be eligible for retreatment.

Packaging and Administration

The T cells will be administered via intravenous infusion over 20-30 minutes without a leukocyte filter.

Autologous co-stimulated T-cell infusion

1. Co-stimulated T-cells will be infused at a dose of approximately 1×10^{10} (+/-20%). If optimal cell dose of 1×10^{10} (+/-20%).) is not achieved, a lower dose of activated T cells that meets release criteria may be infused at the discretion of the Principal Investigator.
2. Patients will receive premedication with Acetaminophen 650 mg PO and/or diphenhydramine 25-50 mg IV at least 30 minutes prior to infusion.
3. Additional orders: Acetaminophen 650 mg PO q4h for temperature > 38°, diphenhydramine 25 mg IVPB q3-4h prn and meperidine 25 mg IVPB q 2h prn for chills (if chills persist inform MD). Anaphylaxis precautions: Following drugs should be available at bedside: 3cc epinephrine 1:1000, diphenhydramine 25 mg IV and hydrocortisone 100 mg IV. In the event of a severe allergic reaction (e.g., anaphylaxis, bronchospasm, hypotension) or serious adverse reaction (i.e., cardiac failure, respiratory failure, severe nausea and vomiting) to the T Cell therapy, the infusion of the autologous T Cells will be stopped immediately and the patient will be provided with the supportive care deemed necessary by the physician and medical staff at the clinic.
4. Optional Procedure: With the patient's consent, if the patient cannot receive the co-stimulated T cells, the cells will remain cryopreserved in the Stem Cell Laboratory indefinitely. The patient can receive the cells at a later date. If the patient's physician feels that the patient will no longer benefit from the cells,

the cells may be used for research or discarded. If the patient refuses, the cells will be destroyed.

Study Enrollment:

The study population for this research will consist of participants from:

Only at MDACC

Estimated Accrual:

Total Accrual at MDACC:	40
Estimated monthly accrual at MDACC:	1

Accrual Comments:

The sample size of 40 patients was chosen for logistical reasons.

Is this an NCI-Cancer Therapy Evaluation Protocol (CTEP)? No

Is this an NCI-Division of Cancer Prevention Protocol (DCP)? No

Statistical Considerations:

Overview

This is a phase II trial of infusion of autologous T cells for immune restoration in patients with CLL. The primary scientific goal is to determine the feasibility and safety of this procedure. A total of 40 patients will receive T cell infusions. Endpoint evaluation will be at day +90 after the co-stimulated T cell infusion.

Sample Size

In this trial, the sample size of 40 patients was chosen for logistical reasons. With 40 patients, a 95% confidence interval around the success rate will be no wider than 32%.

Primary Endpoint

Success will be defined as achievement of a target activated T-cell dose of $1 \times 10^8 \pm 20\%$ and the lack of dose limiting toxicity (DLT).

For this trial DLT is defined as:

- Any grade 4 or higher non-hematologic toxicity or grade 3 or 4 allergy/immunology toxicity;
- Allergic reaction or urticaria grade 3 or higher (CTC v4.03 CTCAE) by +90 days after T cell infusion;
- Grade 2 or greater autoimmune phenomena; or,
- Grade 4 or higher hematologic toxicity (with the exception of any preexisting AE due to prior treatment or due to disease) deemed related to T cells and occurring by day +90 after T cell infusion.

Feasibility is defined as achievement of the target T cell dose ($1 \times 10^8 \pm 20\%$) without DLT in > 50% of patients enrolled.

Safety Monitoring

Any death due to the infusion of co-stimulated T-Cell product itself and not disease progression will be considered unacceptable and the study will be stopped. If the study is not terminated early, it will continue

until all patients have been treated with co-stimulated T Cells and completed all follow up evaluations.

In addition, we will use a Bayesian sequential monitoring rule to monitor the primary endpoint of the study. If there is a high probability that the overall success rate is less than 50%, enrollment into the trial will be stopped. We will enroll a minimum of 6 patients onto the study before stopping. We will use the following criteria: we will stop enrollment if at any time during the course of the trial:

$\Pr [\text{90-day success rate} > 0.50 \mid \text{data}] < 0.025$

That is, if we determine that there is a less than 2.5% chance that the 90-day success rate is greater than 50%, accrual will be stopped. We assume a beta (1, 1) prior distribution for the success rate, which has a mean of 0.50 corresponding to the target success rate. Stopping boundaries corresponding to this probability criterion are to terminate accrual if:

If there are this many patients accrued	Stop the trial if this number of patients meet criteria for success
6-7	0
8-10	0-1
11-13	0-2
14-15	0-3
16-18	0-4
19-21	0-5
22-23	0-6
24-26	0-7
27-28	0-8
29-31	0-9
32-33	0-10
34-35	0-11
36-38	0-12
39	0-13
40	Always Stop

This stopping rule was chosen to assure that the probability that the trial will stop early would be approximately 10% if the true success rate was 50%. The operating characteristics of this rule are shown in the table below.

We will enroll 3 patients and then wait till all 3 have reached +90 days without DLT before enrolling more patients. At that time point 3 additional patients will be enrolled and we will wait till they have all reached

+90 days and without DLT before enrolling the remaining patients.

Operating Characteristics for Success Monitoring Rule

If the true 90-day success rate is...	Early Stopping Probability	Achieved Sample Size		
		25th percentile	50th percentile	75th percentile
0.3	0.833	8	16	32
0.4	0.413	19	40	40
0.5	0.108	40	40	40
0.6	0.018	40	40	40
0.7	0.002	40	40	40

The monitoring rules will be assessed by the study team with assistance as necessary from the Department of Biostatistics at MD Anderson Cancer Center.

Secondary Analyses

Immune reconstitution: We will assess the percentages and absolute values of CD3+, CD4+, CD8+ and CD4/CD8 ratio and report these at each time point along with 95% confidence intervals. In addition, immune reconstitution will be compared at each time point.

Overall Response (CR+PR): We will assess overall response (CR+PR).

Infections: We will assess the rates of infection.

Criteria for Removal from Study:

1. **"Subjects" voluntary withdrawal from protocol.**
2. **Noncompliance of the patient with protocol requirements**
3. **After 5 years of treatment completion**
4. **Subject lost to follow-up**
5. **Decision by the investigators that withdrawing is in the subject's best interest**
6. **Pregnancy**
7. **Termination of the study by the investigator, IRB, or FDA**
8. **Unacceptable toxicity and other safety reasons- as defined by the stopping rules below.**
9. **Patients who experience DLT will not be eligible for retreatment.**

Toxicity Management, Stopping Rules and Study Termination

Only unexpected SAEs that are related to the activated autologous T cells would define a stopping rule.

Management of toxicity

Autoimmune toxicity associated with activated autologous T cells has been managed with a course of pharmacologic immunosuppression such as systemic corticosteroids.

Dose Limiting Toxicity

Dose limiting toxicity (DLT) is defined as any one or more of the following which occur after the T Cell Infusion:

1. Any Grade 3 or higher non-hematological adverse event other than fevers lasting less than 72 hours must will be considered DLT. Any prolonged grade 4 or higher hematologic toxicity (longer than 7 days) due to study treatment will be considered as DLT (CTC v4.03 CTCAE).
2. Allergic reaction or urticaria grade 3 or higher and deemed related to T cells (as determined using the Common Terminology Criteria for Adverse Events v4.03).
3. Grade 2 or greater autoimmune phenomena
4. Grade 4 or higher hematologic toxicity with the exception of any preexisting AE due to prior treatment or due to disease.

Stopping Rules

The statistical considerations section describes the primary stopping rule for the study, a rule which monitors patient success rate.

In addition, accrual to the study will be suspended to allow review with the institutional IRB if any death occurs among subjects who receive investigational agents due to the infusion of co-stimulated T-Cell product itself and not disease progression.

If the study is prematurely halted based on preliminary information, it will be allowed to continue only if it is determined upon review that the incidence of adverse events is not exceedingly high for this patient population and that any death is not primarily due to the co-stimulated T-Cell therapy. If the study is not terminated early, it will continue until all patients have been treated with co-stimulated T Cells and completed all follow up evaluations.

Data Safety Monitoring Board / DSMB at MDACC:

Select the name of the data safety monitoring board (DSMB) monitoring this protocol:
Not Applicable

Please explain:

As of PDOL Version 07, this study is not randomized nor blinded.

Protocol Monitoring:

Does this protocol have a schedule for interim and final analysis? Yes

Provide a summary or schedule of interim analysis.

We will use a Bayesian sequential monitoring rule (Thall et al (ref)) to monitor the primary endpoint of the study. See the Statistical Considerations section for details.

Protocol Monitoring Plan:

Patient registration and monitoring will be performed by the MD Anderson IND Office according to institutional policies.

Intellectual Property:

1. Does this study include any agents, devices, or radioactive compound (or No drug) manufactured at MD Anderson Cancer Center or by a contract manufacturer?

Investigational New Drugs (IND):

Does this protocol require an IND? Yes

Who is the IND Holder/Regulatory Sponsor?

MD Anderson

IND Number: 16501

Please "Compose" an Investigator's Brochure Cover Letter. For technical assistance, contact the PDOL Help Desk, [contact].

Investigational Device (IDE):

Does this study utilize an Investigational Device? No

Moon Shots Program

Will your protocol be funded by the Moon Shots Program? Yes

Specific Disease Site(s): Chronic Lymphocytic Leukemia (CLL)

Platform(s): Applied Cellular Therapy (ACT)

Sponsorship and Support Information:

Does the Study have a Sponsor, Supporter or Granting Agency? Yes

Sponsor Name: Moon Shot Program

Support Type: Other: CLL

This Sponsor/Supporter/Granting Agency will receive data.

Regulatory Requirements

Radioactive Material:

Does this study involve the administration of radioisotopes or a radioisotope labeled agent?

No

[Click here for help](#)

Biosafety:

Does this study involve the use of Recombinant DNA Technology? No

Does this study involve the use of organisms that are infectious to humans? No

Does this study involve human/animal tissue other than blood derived hematopoietic stem cells? Yes

Are you using Tisseel or E vicel or similar? No

Questions should be addressed to the Transfusion Medicine Tissue Coordinator at [contact].

Laboratory Tests:

Is there any biomarker testing in this study being used to determine patient/participant eligibility, treatment assignment, or management of patient/participant care?

Yes
 No
 Not Applicable For This Protocol

Manufacturing:

Will you manufacture in full or in part (split manufacturing) a drug or biological product at the M. D. Anderson Cancer Center for the proposed clinical study? Yes

Please provide the name of the responsible party, the facility or department, contact information and the name of the product or intermediate.

The investigational agent to be administered under this protocol is activated autologous T cells manufactured by in the Cell Therapy Laboratory at the MD Anderson Cancer.

Contact:

[name].
[contact]

Will you obtain an unlicensed (not FDA approved for use in humans) drug or biological product precursor or intermediate for use in patients? Yes

Obtained from a supplier under a manufacturing contract with MDACC

Student/Trainee Information:

Is this research being conducted as a partial fulfillment for completion of a degree? No

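### The stated cell yield tops out at the nominal planned dose, so yield range, dose window, same-dose retreatment and endpoint target need to be reconciled together

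*Combined protocol and SAP*

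**What the plan says.** All of this is in the combined protocol and SAP.

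- **Collection and yield** (Proposed Treatment/Study Plan). "All eligible patients will have 250 cc of whole blood collected via phlebotomy", followed by a 14-day expansion: "The process can generate 2.5×10^9 to 1×10^{10} cells which will be formulated for infusion". Then, as a separate sentence: "Cells for later additional infusions may be cryopreserved". The plan gives no yield distribution, no number of expansion runs and no amount to be frozen.
- **Dose** (same section). The planned single infusion is 1×10^10 ±20%, stated twice. For patients who cannot reach it, "a lower dose of activated T cells that meets release criteria may be infused at the discretion of the Principal Investigator".
- **Retreatment** (same section). Patients who had no DLT and need more cells "may be retreated with previously cryopreserved expanded cells at the same or lower dose level", 6 to 12 months after the first infusion, followed for toxicity only.
- **Endpoint** (Statistical Considerations, Primary Endpoint). "Success will be defined as achievement of a target activated T-cell dose of" 1×10^8 ±20%, together with absence of DLT. Feasibility requires this in more than 50% of enrolled patients.
- **Monitoring** (Statistical Considerations, Safety Monitoring). Accrual stops if the posterior probability that the success rate exceeds 0.50 falls below 0.025, with a beta(1,1) prior and at least 6 patients.

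**The concern.** The dose window is centred on the largest yield the process is said to produce. Its upper half, 1×10^10 to 1.2×10^10, lies above every stated yield, and only the top of the yield range reaches the lower half. The plan also contemplates freezing cells for a later infusion at the same dose, although the stated yield does not cover two doses in the window.

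The endpoint text currently hides the statistical consequence, because its target is 100 times lower than the treatment-plan dose. If that conflict is settled by changing only the exponent in the endpoint, dose attainment becomes a demanding criterion. A patient safely given a permitted lower dose would then count as a failure, both in the feasibility result and in the stopping rule. An early stop for low success could reflect yield alone, and the single success proportion would not show whether toxicity or manufacturing shortfall was the cause.

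**Working it through.** **Inputs.** Yield 2.5×10^9 to 1×10^10; planned dose 1×10^10 ±20% (both Proposed Treatment/Study Plan). Endpoint target 1×10^8 ±20%; feasibility above 50% of enrolled; N = 40 (Statistical Considerations). Stopping boundaries for 6 to 39 patients (Safety Monitoring).

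**1. The plan's own figures.** An exact binomial recursion over the stated boundaries reproduces the operating characteristics:

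| True success rate | Early stop, stated | Early stop, recomputed |
|---|---|---|
| 0.3 | 0.833 | 0.8332 |
| 0.4 | 0.413 | 0.4131 |
| 0.5 | 0.108 | 0.1077 |
| 0.6 | 0.018 | 0.0178 |
| 0.7 | 0.002 | 0.0021 |

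The boundaries and sample-size percentiles also match. The monitoring rule itself is not in question.

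**2. Yield against the planned dose.**
- Window: 0.8 × 10^10 = 8×10^9 to 1.2 × 10^10 = 1.2×10^10.
- Share of the yield range below the floor, linear: (8 − 2.5)/(10 − 2.5) = 73.3%.
- Log scale: ln(8/2.5)/ln(10/2.5) = 83.9%.
- Part of the window within stated yields: (10 − 8)/(12 − 8) = one half.

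These are shares of a range, not of patients.

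**3. Two infusions from one yield.**
- Both in the window: at least 2 × 8×10^9 = 1.6×10^10, against a maximum of 1×10^10.
- Left after a first dose of 8×10^9: at most 1×10^10 − 8×10^9 = 2×10^9.
- Largest equal pair: 1×10^10 / 2 = 5×10^9 each.

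**4. Yield against the endpoint target as written.** The window is 0.8×10^8 to 1.2×10^8. The lowest yield is 2.5×10^9 / 1.2×10^8 = 21 times its upper limit, and the highest is 83 times. Yield does not bind.

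**5. If the endpoint target were 1×10^10 ±20%.** With no DLT, and taking 1×10^10 as the most a lot can yield, the success rate is at most P(yield ≥ 8×10^9). Exceeding 50% then needs more than half of lots within 20% of the maximum. The documents give no distribution, so the rows below are assumptions for illustration, with no DLT and nothing frozen:

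| Assumed yield distribution | P(yield ≥ 8×10^9) | Early stop | P(more than 20 of 40) |
|---|---|---|---|
| Even on log scale | ln(1.25)/ln(4) = 16.1% | 0.999 | below 0.001 |
| Even | 2.0/7.5 = 26.7% | 0.92 | 0.0005 |
| Triangular, peak at the maximum | 1 − (5.5/7.5)² = 46.2% | 0.19 | 0.26 |

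The last column is the plain binomial tail, ignoring early stopping. A distribution packed closer to the maximum would do better still. If 60% or 70% of lots reached the window, the plan's own table gives early stopping of 0.018 or 0.002.

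**The case against.** The strongest reply is that the endpoint is written at 1×10^8 ±20%, where yield is not limiting. A reader might infer that the plan's own figures point to an early stop for low success. They do not: that needs both a target of 1×10^10 and an assumed yield distribution, and the documents supply neither. With no median or patient data, they are compatible with anything from near-certain stopping to almost none. This objection stands, so the endpoint consequence is conditional.

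A reader might also infer that same-dose retreatment is arithmetically impossible. That is too broad. It fails only for patients first dosed within the window and resupplied from the same stated yield. Lower retreatment doses are allowed, and equal doses up to 5×10^9 fit the maximum. This relief is limited, however: lower first doses are meant for patients who cannot reach the planned dose, and infusing all their cells would leave none to freeze.

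The wording also leaves room. The yield is what the process can generate, which need not be a hard ceiling. A single expansion run is not stated, nor whether the range includes frozen cells, nor that freezing takes priority over the first dose. These are gaps for the sponsor to close; they do not make the stated figures agree.

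Finally, a feasibility endpoint should fail when manufacture misses its target, and a negative result could be broken down into dose and DLT afterwards. Both are fair. What remains is that the plan does not commit to that breakdown.

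**Conclusion.** The concern holds in a limited form. On the stated figures alone, the maximum yield equals the nominal planned dose, 73% of the range (84% on the log scale) is below the dose floor, and two in-window infusions need at least 1.6 times the maximum yield. The retreatment shortfall does not depend on the endpoint wording. It does assume that both infusions come from one stated yield and that 1×10^10 is its ceiling.

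The effect on feasibility is conditional on the endpoint target being aligned to 1×10^10. In that case more than half of lots must come within 20% of the stated maximum, and the documents offer no evidence either way. The early-stopping figures of 0.92 and 0.999 illustrate two assumed distributions and do not predict this trial's outcome. The conflict between 10^8 and 10^10 is the larger defect, and the two matters should be settled together, since correcting the endpoint alone would expose this one.

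**What to change.** Reconcile four items across the Proposed Treatment/Study Plan and the Primary Endpoint section: the yield range, the dose window, the same-dose retreatment wording and the endpoint target. The sponsor decides which figures stand; no dose is proposed here. The text should also say whether the yield range is a ceiling, whether it includes cells to be frozen, and whether it refers to one expansion.

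Keep the dose component of the primary endpoint as the dose actually infused. Scoring it on total harvest would redefine both the endpoint and what the stopping rule monitors, and could count a patient infused below the window as a success. Report alongside it, among enrolled patients:

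- (a) the proportion reaching the target dose;
- (b) the proportion infused with any released lot, at any dose, without DLT;
- (c) the proportion whose total harvest, before any freezing, reached the window, with the distribution of harvests.

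Together these separate manufacturing shortfall from toxicity, and (c) shows whether freezing cells affected dose attainment. The cost is protocol wording and a few descriptive summaries from manufacturing and toxicity records. The downside is a less simple headline result.

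### The plan takes patients with a DLT off study, which read literally ends their infection and safety follow-up for an outcome-related reason

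*Combined protocol and SAP*

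**What the plan says.** The second of the Secondary Objectives reads: "To study the incidence of infections for up to 1 year following activated T cell infusion".

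The Proposed Treatment/Study Plan section gives the treatment: "Patients will receive a single infusion of ex-vivo expanded autologous T-Cells". It then allows a further infusion for patients who later need one:

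- on timing: "Retreatment will occur 6-12 months after the first infusion as long as no DLT was noted with the first infusion";
- on follow-up: "These patients will be only followed for toxicity";
- on patients with a DLT: "Patients who have previously experienced DLT will be removed from the study and will not be eligible for retreatment".

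Other sections bear on the same patients:

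- Criteria for Removal from Study, item 9: "Patients who experience DLT will not be eligible for retreatment".
- The same list, item 3, sets the ordinary end of participation: "After 5 years of treatment completion".
- Safety Monitoring and Stopping Rules both say that, unless the study is terminated early, "it will continue until all patients have been treated with co-stimulated T Cells and completed all follow up evaluations".

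For analysis, the Secondary Analyses section says only that infection rates will be assessed. It names no denominator and no rule for patients whose follow-up stops early.

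**The concern.** The retreatment paragraph attaches two consequences to a DLT: leaving the study and losing access to a second infusion. Since one infusion is the planned treatment, leaving the study appears to mean more than not being retreated. The natural literal reading is that data collection stops.

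The patients affected are chosen by an event that follows infusion. Their later infections, late toxicity, immune recovery and response would go unrecorded because of how they fared. An infection rate that drops them, or censors them at removal, then rests on their later risk matching that of the patients who stayed. The documents give no basis for that assumption. They offer some reason to doubt it: autoimmune phenomena of grade 2 or more count as DLTs, the section on managing toxicity says autoimmune toxicity has been treated with immunosuppression, and the Rationale links immunosuppression to infection.

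For a safety and feasibility trial, the patients with the worst tolerance are also those in whom later safety data matter most.

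**Working it through.** **The plan's own figure.** None is given for infection. The only precision statement is that, with 40 patients, a 95% interval for the success rate is no wider than 32%. At a rate of 0.5 the Wald width is 2 × 1.96 × √(0.25/40) = 31.0%; Wilson gives 29.6% and the exact interval at 20/40 gives 32.4%. The figure is sound to rounding, and serves below only as a yardstick.

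**The texts compared.**

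- The study plan removes DLT patients from the study.
- Item 9 of the removal list bars retreatment only. It does sit under a heading about leaving the study, and item 8 lists unacceptable toxicity as a removal reason by reference to the stopping rules, so the list does not clearly favour the narrow reading.
- Safety Monitoring and Stopping Rules speak of all patients completing follow-up, but do not say which evaluations a removed patient still owes.

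No sentence says that follow-up continues after a DLT.

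**Window lost after a DLT.** For removal on or before day +90: (365 − 90)/365 = 275/365 = 75% or more of the infection window.

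**Window affected by retreatment.** At 6 months, (12 − 6)/12 = 50% of the window; at 12 months, none. The loss may be partial, because toxicity follow-up could record some infections as adverse events.

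**Effect on the estimate.** Take infection by 1 year as yes or no (my simplification). With *x* infected among those of known status and *m* unknown, the best and worst cases are *x*/40 and (*x* + *m*)/40. The width is *m*/40, or 2.5 points per patient. This is a maximum: a patient with an infection already recorded has known status.

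**Illustration with assumed DLT rates.** The enrolment rule requires two groups of 3 to reach day +90 without DLT before the rest enter. In a trial that reaches 40, day-90 DLTs therefore fall among 40 − 6 = 34.

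| Assumed DLT rate | Expected DLTs in 34 | Maximum width of bounds | Chance first 6 are DLT-free |
|---|---|---|---|
| 5% | 1.7 (about 2) | 2/40 = 5 points | 0.95⁶ = 0.74 |
| 10% | 3.4 (about 3) | 3/40 = 7.5 points | 0.90⁶ = 0.53 |
| 20% | 6.8 (about 7) | 7/40 = 17.5 points | 0.80⁶ = 0.26 |

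Against a maximum sampling width of 31.0 points, the first row is small and the last is not negligible.

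**Direction.** If a share *d* is removed and dropped from the analysis, the error is −*d* × (risk with DLT − risk without). With assumed *d* = 10% and risks of 60% and 40%, it is −2 points; with *d* = 20% and risks of 80% and 40%, −8 points; with equal risks, zero. If DLT patients had the lower risk, the sign would reverse.

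**Primary endpoint.** A DLT by day +90 is already a failure, and retreatment starts no earlier than 6 months. Neither rule changes day +90 success or the monitoring of it.

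**The case against.** The case against has several parts, and some of it stands.

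- **One phrase carries the point.** Removal from the study after a DLT is stated once, in a paragraph about retreatment, and may have meant only no further study treatment. That is possible, and is why the claim is limited to the text as written. It does not dispose of the point: the sections differ, and site staff could follow either.
- **The toxicity-only sentence may concern the repeat infusion alone,** leaving follow-up from the first infusion intact. This is an ordinary reading. A reader might infer that retreated patients certainly drop out of infection follow-up; the documents do not establish that, so this part is only a possibility.
- **The plan speaks of infection rates over up to a year, not a yes/no status at 1 year.** Correct. The bounds depend on my recasting. A rate over observed time tolerates unequal follow-up, but is still biased if dropout is related to risk.
- **A severe infection may itself be a DLT.** Under the Dose Limiting Toxicity section, grade 3 or higher non-hematological events count, short fevers aside. Such a patient's status would be known, and only later infections would be lost. The tabulated widths are therefore upper limits.
- **Silence is weak evidence** in an abstract-style document that shows no visit calendar. This is fair, but the point rests on an explicit removal statement as well as on silence.
- **Infection is a descriptive secondary objective** with no test or decision attached. True, and this limits the weight of the point.

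A reader might also infer that incidence in all infused patients must be the main estimate. That is a choice of estimand. Restricting the estimate to the period before a second infusion is also defensible, provided it is stated. The differing DLT definitions in the Primary Endpoint and Dose Limiting Toxicity sections need reconciling and determine who is affected, but they are a separate matter and lend no support here.

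**Conclusion.** The point holds in a limited form, centred on removal after a DLT. The study plan and the removal list say different things about these patients. Followed literally, the study plan stops data collection because of a post-infusion outcome, so the missing follow-up cannot be assumed uninformative. The loss is at least 75% of the infection window for a patient removed by day +90. Retreatment may add a loss of up to half the window per retreated patient, on one of two tenable readings.

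The overall effect cannot be sized from the documents. Each patient of unknown status costs at most 2.5 points of best/worst-case width among 40; the 5 to 17.5 point range rests on assumed DLT rates of 5-20%, full accrual and no infection before removal. It would go too far to conclude that the infection rate will be understated, since the direction depends on risks the documents do not give. It would also be wrong to infer any damage to the day +90 primary endpoint. This should be corrected, but it does not threaten the trial's main conclusion.

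**What to change.** - Reconcile the study plan with items 3 and 9 of Criteria for Removal from Study and with the Safety Monitoring and Stopping Rules text, treating loss of eligibility for retreatment and the end of data collection as two separate things.
- State that every infused patient stays in data collection for safety and infection to 1 year after the first infusion, and for the other secondary endpoints, whatever happens as to DLT or retreatment, unless consent is withdrawn.
- Say whether toxicity-only follow-up refers to the repeat infusion alone, and how infection follow-up after retreatment enters the analysis.
- Beside the infection rate, report the numbers with a DLT, retreated, and with incomplete 1-year infection follow-up.

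The cost is a wording amendment and a little extra data collection in these patients, well inside the 5-year limit already set. The abstract page marks this version as terminated; if data collection has closed, the wording change cannot recover what was not recorded, but the reporting step still applies.
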